Device:	The CardioMEMS HF System consists of a wireless, battery-less pressure sensor implanted into the pulmonary artery and an external electronics that powers and communicates with the sensor and transmits pulmonary artery pressure waveforms and measurements to a secure website for Investigator review and patient management.
Purpose:	The purpose of this Post Approval Study (PAS) is to evaluate the use of the CardioMEMS HF System in patients with Class III Heart Failure (HF) in a commercial setting.
Objective:	The objective of this PAS is to confirm safety and effectiveness in a commercial setting.
Study Population:	
Adults with New York Heart Association (NYHA) Class III Heart Failure who have experienced a heart failure hospitalization within the past 12 months. At least 35% of the enrolled patients will be women.
 
The patients will serve as their own historical controls for effectiveness (1 year prior implantation).
 
All subjects who sign the informed consent form and satisfy the inclusion/exclusion criteria.
 
Ejection fraction data must be taken within the last 3 months to enroll in the study.

Study Design:	
This is a prospective, multi-center, open-label trial conducted in the United States (US).
 
All subjects who sign the informed consent form and satisfy the inclusion/exclusion criteria will be enrolled into the CardioMEMS HF System PAS and will be scheduled for follow-up visits at 1 month and every 6 months for 2 years.
 
Following sensor implant and hospital discharge, subjects will take PA pressure measurements on a daily basis, or as directed by the investigator. These measurements will be automatically transmitted to the secure Patient database (CardioMEMS HF website).

Timeline:	Study visits will be scheduled at Month 1, Month 6, and every 6 months thereafter for 2 years or until study termination.

This confidential document is the property of Abbott and shall not be reproduced, distributed, disclosed or used without the express written consent of Abbott

Clinical Investigation Plan

Number of Subjects	Twelve hundred subjects will be enrolled with at least 35% of the enrolled patients being women (420 women out of 1200). Enrollment will be limited to 15% of the total study population at any one site.
Number of Sites:	This is a prospective, multi-center, open-label clinical trial to be conducted at up to 150 sites.

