7.1. Inclusion Criteria

1. Written informed consent obtained from subject or legal representative
2. ≥ 18 years of age
3. Diagnosis of NYHA Class III Heart Failure *Note: Subjects who are on continuous inotropic therapy should be considered in Stage D refractory heart failure and are not eligible for enrollment in the study.*
4. At least 1 HF hospitalization within 12 months of Baseline visit
5. Subjects with reduced LVEF heart failure should be receiving a beta blocker for 3 months and an ACE-I or ARB for one month unless in the Investigator's opinion, the subject is intolerant to beta blockers, ACE-I or ARB.
6. Subjects with a BMI ≤ 35 . Subjects with BMI >35 will require their chest circumference to be measured at the axillary level, if > 65 inches the patient will not be eligible for the study.
7. Subjects with pulmonary artery branch diameter ≥ 7 mm - (implant target artery - assessed during the RHC)
8. Subjects willing and able to comply with the follow-up requirements of the study

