12.2. Sample Size Considerations

Effectiveness Sample Size Determination

For the primary effectiveness endpoint of HF hospitalization rate during 1 year, 300 patients will provide greater than 90% power to meet the efficacy goal (upper confidence limit less than the HF hospitalization rate in the year prior to enrollment), using a one-sample, two-sided Poisson confidence interval with alpha of 0.05.

Safety Sample Size Determinations

For the two-year primary safety endpoint of freedom from device-related complications, using an exact two-sided test for one-sample binomial proportions with alpha of 0.05, a sample size of 619 subjects will provide greater than 90% power to detect a difference as small as 5% from the null proportion rate of 0.80 (i.e., objective performance criterion of 80%). For sensor failures at 2 years, a sample size of 663 subjects provides greater than 90% power to detect a difference as small as 3.5% from the null proportion rate of 0.90 (i.e., objective performance criterion of 90%).

This confidential document is the property of Abbott and shall not be reproduced, distributed, disclosed or used without the express written consent of Abbott

Clinical Investigation Plan

Thus, the sample size for this study is driven by the safety endpoints. The 2 year attrition rate in CHAMPION was 49.1% (228/550). To ensure sufficient patients are enrolled to adequately evaluate safety and efficacy, 1200 subjects will be enrolled.

Note that at least 35% of the 1200 enrolled patients (420) must be women resulting in approximately 206 women completing the trial (assuming a 49% attrition rate). This sample size will provide greater than 90% power to meet the goal for effectiveness. Regarding freedom from device-related complications and freedom from sensor failures, 206 women will provide greater than 90% power to detect a difference as small as 0.06 from the null proportion rate of 0.90.

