12.7.1. Primary Effectiveness Endpoint

The primary time point for analyses is 12 months post-enrollment. The primary effectiveness endpoint will compare the annualized HF hospitalization rate parameter, γ , at 1 year versus the HF hospitalization rate in the year prior to enrollment using a two-sample, two-sided Poisson confidence interval. If the two-sided, upper 95% confidence interval for the PAS rate parameter is less than that in the year prior to enrollment, then the primary effectiveness endpoint will be met.

Mathematically stated, the primary effectiveness hypothesis is:

$$H_0: \gamma_{(12 \text{ month HF Hospitalization Rate})} \geq \gamma_{(\text{HF hospitalization rate in year prior to enrollment})}$$

$$H_a: \gamma_{(12 \text{ month HF Hospitalization Rate})} < \gamma_{(\text{HF hospitalization rate in year prior to enrollment})}$$

where $\gamma_{(12 \text{ month HF Hospitalization Rate})}$ = the HF hospitalization rate parameter at 1 year in the PAS and $\gamma_{(\text{HF hospitalization rate in year prior to enrollment})}$ = the HF hospitalization rate in the year prior to enrollment.

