12.7.2. Supplemental Analyses

Mortality

The mortality rate over 1 year in study will be reported. Plotting and analysis of survival data will be displayed using Kaplan-Meier methods.

HF Hospitalization or Death

The annualized HF hospitalization or death rate parameter, λ , at 1 year will be compared to the HF hospitalization rate in the year prior to enrollment using a two-sample, two-sided Poisson confidence interval. If the two-sided, upper 95% confidence interval for the PAS rate parameter is less than that in the year prior to enrollment, then the hypothesis will be met.

Mathematically stated, the hypothesis is:

$$H_0: \lambda_{(12 \text{ month HF Hospitalization or Death Rate})} \geq \lambda_{(\text{HF hospitalization rate in year prior to enrollment})}$$

$$H_a: \lambda_{(12 \text{ month HF Hospitalization or Death Rate})} < \lambda_{(\text{HF hospitalization rate in year prior to enrollment})}$$

where $\lambda_{(12 \text{ month HF Hospitalization or Death Rate})}$ = the HF hospitalization or death rate parameter at 1 year in the PAS and $\lambda_{(\text{HF hospitalization rate in year prior to enrollment})}$ = the HF hospitalization rate in the year prior to enrollment.

Patient Compliance

Patient device usage over the course of the trial will be examined. The total number of PA pressure readings taken will be reported as a percentage of patient days at home.

This confidential document is the property of Abbott and shall not be reproduced, distributed, disclosed or used without the express written consent of Abbott

Clinical Investigation Plan

Training Evaluation

To assess the effectiveness of the training program, the safety and effectiveness results will be reported for:

- 1) Academic Hospitals
- 2) Community Hospitals

Subgroup Analyses

The effectiveness analyses will be evaluated in each of the following subgroups:

- 1) Women
- 2) Men
- 3) Reduced Ejection Fraction (< 40%)
- 4) Preserved Ejection Fraction ($\geq 40\%$)
- 5) Ischemic Etiology
- 6) Non-ischemic Etiology
- 7) With ICD/CRT-D
- 8) Without ICD/CRT-D

Quality of Life Evaluations

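### The primary effectiveness rule names a two-sample Poisson interval but decides on the in-study upper limit alone, and neither procedure reflects paired counts selected on a prior event

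*Combined protocol and SAP*

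**What the plan says.** Section 12.7.1 sets the in-study rate at 1 year "versus the HF hospitalization rate in the year prior to enrollment using a two-sample, two-sided Poisson confidence interval". The sentence that follows takes the upper limit of the two-sided 95% interval "for the PAS rate parameter is less than that in the year prior to enrollment, then the primary effectiveness endpoint will be met". Section 12.7.2 uses the same method and the same rule for HF hospitalization or death ("for the PAS rate parameter is less than that in the year prior to enrollment, then the hypothesis will be met"). For subgroups it adds: "The effectiveness analyses will be evaluated in each of the following subgroups".

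Section 12.2 sizes this endpoint at 300 patients for more than 90% power, "using a one-sample, two-sided Poisson confidence interval with alpha of 0.05". It states no rate for either year. For the 206 women it describes as completing the trial, it says: "This sample size will provide greater than 90% power to meet the goal for effectiveness".

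Two design features bear on the analysis. The Synopsis says: "The patients will serve as their own historical controls for effectiveness (1 year prior implantation". Section 7.1 requires: "At least 1 HF hospitalization within 12 months of Baseline visit". The plan gives no pairing, clustering or dispersion term for this endpoint. Mixed models appear in 12.7.2 only for quality of life.

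**The concern.** An interval for the in-study rate is not a two-sample interval. It treats the prior-year rate as a known number, although that rate is estimated from the same patients. A statistician programming 12.7.1 has two rules to choose from, and they demand different gaps between the years.

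The data also fit neither rule well. Each patient contributes to both years, so the counts are paired. The prior-year count cannot be zero, so its variance is below Poisson when the underlying rate is constant. If risk varies between patients or between years, a Poisson variance can be too small. At stake is whether the reported intervals have the coverage they claim. This matters most in the eight subgroups, where samples are smaller, because section 14 sends effectiveness results to FDA and into device labeling.

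**Working it through.** **1. The plan's own figure.** The claim of 300 patients for more than 90% power cannot be reproduced, because 12.2 gives no rates. The one-sample method can be checked on section 13.4 (0.52 against 0.75): exact Poisson power is 85.7% at 114 patients (stated 85%) and 90.5% at 130 (stated 90%). Borrowing those rates for 300 patients gives 99.9% with the one-sample rule. For two independent Poisson samples, 0.23/√((0.52 + 0.75)/300) = 3.54, and Φ(3.54 − 1.96) gives 94.2%. The claim is not contradicted.

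**2. The two rules.** Let a and b be the in-study and prior-year event totals, with one year per patient in each period. In normal approximation:
- literal rule: b − a > 1.96√a
- two-sample interval: b − a > 1.96√(a + b)

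When a and b are close, the second gap is √2 = 1.41 times the first.

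**3. Error at a true in-study/prior ratio of 1, pure Poisson, prior count at least 1.** The underlying rate μ is an assumption. The prior-year mean is m = μ/(1 − e^−μ) and its variance/mean ratio is v = 1 + μ − m. The literal rule errs with probability Φ(−1.96/√(1 + v)), the two-sample interval with Φ(−1.96√2/√(1 + v)).

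| μ | m | v | Literal rule | Two-sample |
|---|---|---|---|---|
| 0.75 | 1.42 | 0.329 | 4.5% | 0.8% |
| 1.0 | 1.58 | 0.418 | 5.0% | 1.0% |
| 1.5 | 1.93 | 0.569 | 5.9% | 1.3% |

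Nominal is 2.5%. The two written rules miss it in opposite directions.

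**4. The same error with dispersion.** The documents give no dispersion, so gamma-Poisson dispersion of 0.5–2 is assumed. Simulation used 206, 300 and 1200 patients and μ of 0.75–1.5.

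| Patient risk across the two years | Literal rule | Two-sample | Patient-clustered ratio |
|---|---|---|---|
| Fully shared (stable) | 5.6–8.2% | 1.1–2.6% | 2.2–3.0% |
| Half shared | 6.9–18.7% | 1.8–10.9% | 1.8–3.1% |
| Independent (extreme) | 9.5–27.0% | 3.7–19.7% | 2.2–3.2% |

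With pure Poisson counts the clustered ratio gave 2.3–2.8%. A separate rerun at 300 patients gave 2.0–3.7% for the clustered ratio over all scenarios (Monte Carlo standard error about 0.3 points).

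**5. No device effect.** Selection on a prior event lowers the ratio by itself. For pure Poisson counts it is 1 − e^−μ, or 0.53–0.78. Over all scenarios it is 0.37–0.88. At 1200 patients every method then passed in every run. At 206 the literal rule passed 81–100% of the time, the two-sample interval 61–100% and the clustered ratio 63–100%.

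**6. Power.** With a true 20% device reduction on top of that selection, the clustered ratio passed 1000 of 1000 runs at 206 patients in every scenario.

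**7. Women.** Section 12 defines enrollment as a successful implant, and 12.1 analyses all implanted subjects regardless of completion, at 12 months. The women's effectiveness set is therefore about 0.35 × 1200 = 420, not 206.

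**The case against.** The strongest reply is that this is a wording slip. The prior-year rate could be read as a fixed benchmark, these patients' observed history, which makes a one-sample comparison coherent. That reading is available, but it contradicts the named two-sample method, and the in-study interval would still carry no between-patient dispersion. A reader could also take the comparator to be the prior-year upper limit. The rule would then still not be an interval for a ratio or difference.

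Second, the two-sample interval that 12.7.1 names is not badly behaved. It is conservative with pure Poisson counts and at or near nominal when patient risk is stable. It becomes anti-conservative only with period-specific dispersion, which is assumed. This stands, so a claim that neither rule has a usable error rate would go too far.

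Third, an in-study/prior ratio of 1 is not the case of an inert device. Under pure Poisson counts it needs a device that raises the rate by 28% to 89% (1/0.78 to 1/0.53). This also stands. The figures in steps 3 and 4 measure interval validity, not the chance of passing an ineffective device.

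A reader might also infer that the power claims of more than 90% in 12.2 fail. Power does look low if the true ratio is set at 0.80, but entry selection alone often takes the ratio below that, so 0.80 often implies harm. With a real 20% reduction the claims hold under these assumptions.

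**Conclusion.** The conflict between the named method and the decision rule is on the page, in both 12.7.1 and 12.7.2, and does not depend on any assumption. The literal rule omits the sampling error of the prior-year rate. With pure Poisson counts that puts its one-sided error at 4.5–5.9% against 2.5%, for assumed underlying rates of 0.75–1.5. Larger figures need assumed dispersion. The 8.3% from 1 − Φ(1.96/√2) applies to two independent samples without the entry rule, which is not this design.

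The consequence is for the validity of the reported intervals, mainly in subgroups. A reader might infer that the primary conclusion is in doubt because of the choice of rule. The calculations do not support this: at 1200 patients every method passes even with no device effect, through regression to the mean. That is a separate limitation, which no change of interval removes. Nor is there a case that the sub-study is underpowered. Its plain Poisson interval against 0.75 + 0.10 = 0.85 lacks a dispersion term, but any shortfall would rest on assumed dispersion. The change is worth making, but it does not decide the trial's result.

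**What to change.** Replace the decision sentence in 12.7.1 and 12.7.2, and apply the same rule to the subgroups: *met if the upper limit of the two-sided 95% confidence interval for the in-study/prior-year rate ratio is below 1, from a log-link model of patient-period counts with log follow-up time as offset, period as covariate and variance clustered on patient.* Report the result of the version C rule alongside.

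In 12.2, align the sizing method with this rule and state the assumed rate for each year. Base the women's effectiveness statement on all implanted women, about 420. As an option, use a robust log-scale variance for the sub-study in 13.9.2, keeping 0.85 as the fixed goal.

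No new data or patients are needed. The cost is procedural: section 17.2 requires IRB approval and FDA submission for changes affecting validity. Version C is dated 19 February 2018, after the planned end of enrollment in December 2017 (Appendix A), and this open-label study already reports results to FDA at intervals. A late change to the primary rule will draw questions, which is why the version C result should be shown beside it.

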12.7.2. Supplemental Analyses

Mortality

The mortality rate over 1 year in study will be reported. Plotting and analysis of survival data will be displayed using Kaplan-Meier methods.

HF Hospitalization or Death

The annualized HF hospitalization or death rate parameter, λ , at 1 year will be compared to the HF hospitalization rate in the year prior to enrollment using a two-sample, two-sided Poisson confidence interval. If the two-sided, upper 95% confidence interval for the PAS rate parameter is less than that in the year prior to enrollment, then the hypothesis will be met.

Mathematically stated, the hypothesis is:

$$H_0: \lambda_{(12 \text{ month HF Hospitalization or Death Rate})} \geq \lambda_{(\text{HF hospitalization rate in year prior to enrollment})}$$

$$H_a: \lambda_{(12 \text{ month HF Hospitalization or Death Rate})} < \lambda_{(\text{HF hospitalization rate in year prior to enrollment})}$$

where $\lambda_{(12 \text{ month HF Hospitalization or Death Rate})}$ = the HF hospitalization or death rate parameter at 1 year in the PAS and $\lambda_{(\text{HF hospitalization rate in year prior to enrollment})}$ = the HF hospitalization rate in the year prior to enrollment.

Patient Compliance

Patient device usage over the course of the trial will be examined. The total number of PA pressure readings taken will be reported as a percentage of patient days at home.

This confidential document is the property of Abbott and shall not be reproduced, distributed, disclosed or used without the express written consent of Abbott

Clinical Investigation Plan

Training Evaluation

To assess the effectiveness of the training program, the safety and effectiveness results will be reported for:

- 1) Academic Hospitals
- 2) Community Hospitals

Subgroup Analyses

The effectiveness analyses will be evaluated in each of the following subgroups:

- 1) Women
- 2) Men
- 3) Reduced Ejection Fraction (< 40%)
- 4) Preserved Ejection Fraction ($\geq 40\%$)
- 5) Ischemic Etiology
- 6) Non-ischemic Etiology
- 7) With ICD/CRT-D
- 8) Without ICD/CRT-D

Quality of Life Evaluations

Patient improvement in Quality of Life will be reported. The difference between the Quality of Life scores at 6 months, 12 months, 18 months, and 24 months will be compared to the baseline values using general linear mixed models. Quality of Life will be measured using the Kansas City Cardiomyopathy Questionnaire-12 (KCCQ-12), the Brief Illness Perception Questionnaire, and the Cardiac Health Security Survey.

PAS SUB-STUDY

This section describes the design, hypotheses, populations, endpoints and analysis of the PAS sub-study. All other sections of the protocol pertain to the main PAS cohort unless specifically stated otherwise.

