	
The effectiveness population consists of all subjects who received a sensor implant regardless of study completion status.
 
Supplemental Analyses
 
Mortality at 1 year will be analyzed. Plotting and analysis of mortality will be displayed using Kaplan-Meier methods.
 
The annualized HF hospitalization or death rate at 1 year in study will be compared to the HF hospitalization rate in the year prior to enrollment.
 
Patient compliance over the trial will be examined. The total number of pulmonary artery (PA) pressure readings taken will be reported as a percentage of patient days at home.
 
To assess the effectiveness of the training program, the safety and effectiveness results will be reported for Academic Hospitals and Community Hospitals.
 
Effectiveness analyses will be performed by the following subgroups: Women, Men, Reduced Ejection Fraction (< 40%), Preserved Ejection Fraction ($\geq 40\%$), Ischemic Etiology, Non-ischemic Etiology, With ICD/CRT-D, and Without ICD/CRT-D.

Reporting of Interim and Primary Analyses	
In addition to the primary safety and effectiveness analyses, updates from the PAS will be submitted to FDA as a PMA supplement every 6 months for the first two years of the study (annually thereafter) and updated in the device labeling. This information will include the following: study enrollment and follow-up status; demographic information; safety and effectiveness results; mortality; serious adverse events; days alive outside of the hospital for heart failure; patient compliance; sensor performance; and medication changes in response to PA pressure.
 
The primary safety analyses will be reported after all patients complete 24 months post enrollment or discontinue early. The primary effectiveness analyses will be reported after all patients complete 12 months post enrollment or discontinue early.

Version:	C
Date:	19 February 2018

SUB-STUDY PROTOCOL SYNOPSIS

Sub-Study Purpose:	The purpose of this sub-study is to evaluate the use of the CardioMEMS™ HF System in a commercial setting in patients with NYHA Class III heart failure who are optimally managed and are clinically similar to the Control group in the CHAMPION study based on pre-enrollment data.
--------------------	---

This confidential document is the property of Abbott and shall not be reproduced, distributed, disclosed or used without the express written consent of Abbott

Clinical Investigation Plan

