4.4. CardioMEMS HF System

The CardioMEMS™ HF System provides PA hemodynamic data used for the monitoring and management of HF patients. The system measures changes in PA pressure which physicians use to initiate or modify heart failure treatment.

[figure not shown]
The system includes the following components:

- Implantable wireless sensor with delivery catheter
- Patient or hospital electronics system
- Patient database (CardioMEMS HF Website)

This confidential document is the property of Abbott and shall not be reproduced, distributed, disclosed or used without the express written consent of Abbott

Clinical Investigation Plan

Figure 1. CardioMEMS HF System

The system provides the physician with the patient's PA pressure waveform including systolic, diastolic, and mean pressures as well as heart rate. The Sensor is permanently implanted into the distal PA using transcatheter techniques in the catheterization laboratory; the sensor baseline is set to the mean PA pressure using a pulmonary artery catheter. Daily PA hemodynamic measurements are taken by the patient in a supine position at home. The patient measurement system consists of an antenna and electronics unit that guides the patient through the short reading process. The data can be recorded from the home, hospital, physician's office, or clinic. The hemodynamic data is transmitted to the website which is accessible via a secure website to the patient's physician or nurse.

Implantable Sensor

The sensor measures pulmonary artery pressure using MEMS (micro-electromechanical systems) technology and requires neither batteries nor leads. It is silicon wafer fabricated and measures 15 mm in length, 3.4 mm in width and 2 mm in thickness. The sensor is permanently implanted in a branch of the left or right pulmonary artery via a catheter. The Patient Electronics Unit provides both wireless communication and power to the sensor.

Implantable Sensor Delivery System

This confidential document is the property of Abbott and shall not be reproduced, distributed, disclosed or used without the express written consent of Abbott

Clinical Investigation Plan

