Implanted subjects will be evaluated at Month 1 (± 7 days) and at Months 6, 12, 18, and 24 (± 30 days) and the following procedures/assessments will be performed:

- Updated medical and surgical history
- Assessment of AEs that occurred since the last visit
- Abbreviated physical examination (significant changes since previous visit) including vital signs (heart rate, respiratory rate, blood pressure), and weight
- Assessment of NYHA functional class
- Kansas City Cardiomyopathy Questionnaire (KCCQ-12)
- Brief Illness Perception Questionnaire
- Cardiac Health Security Survey
- Heart failure medication review
- PA pressure measurements may be obtained at the Investigator's discretion

This confidential document is the property of Abbott and shall not be reproduced, distributed, disclosed or used without the express written consent of Abbott

Clinical Investigation Plan

Subjects will be reminded to obtain pulmonary artery pressure measurements utilizing the CardioMEMS HF System as directed. Subjects will be reminded of the current ACC/AHA guidelines regarding sodium and fluid restrictions.

The study coordinator or designee will administer patient-reported outcome questionnaires. It is important that the subject understands the meaning of all words and instructions in each questionnaire and answers all the questions. The subject will be instructed to ask any questions about the questionnaire if further explanation is needed. The research coordinator or designee will review the questionnaires to verify that all questions have been answered. The Patient Reported Outcomes will be obtained at 6, 12, 18 and 24 months. Patients who were enrolled in the study prior to addition of patient reported outcome questionnaires, and therefore did not complete baseline questionnaires, are not required to complete questionnaires at the follow-up visits.

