8.5. PA Pressure Readings in the Hospital

If a subject is hospitalized, seen in the emergency room (ER) or has a clinic visit, the CardioMEMS HF System may be used to obtain pulmonary artery pressure measurements at the investigators discretion. Following sensor implant, subsequent RHC procedures or pulmonary artery catheter insertions must be performed under fluoroscopic guidance.

Resetting of the sensor baseline will be performed as deemed necessary by Sponsor. Baseline resetting may require an echocardiogram or a RHC procedure.

Following the sensor implant, should a RHC procedure or PA catheter evaluation be clinically warranted, comparative pulmonary artery pressures utilizing the CardioMEMS HF System should also be obtained utilizing the hospital electronics unit.

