10.2.3. Patient Compliance

Patient device usage over the course of the trial will be examined.

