	Subjects	Events	Subjects	Events	Subjects	Events	Subjects	Events
All Patients with an Event	XX (XX.X%)	XXX	XX (XX.X%)	XXX	XX (XX.X%)	XXX	XX (XX.X%)	XXX
System Organ Class I	XXX	XXX	XXX	XXX	XXX	XXX	XXX	XXX
...								

Days alive outside of hospital for heart failure

	6 Months N=XXXX	12 Months N=XXXX	18 Months N=XXXX	24 Months N=XXXX
	N	N	N	N
Days Alive outside of Hospital	XXX	XXX	XXX	XXX

Weekly Patient Pressure Reading Compliance

	Compliance %
Mean \pm StdDev	XX.X \pm XX.X%
Median	XX.X%

Sensor Performance

	N	Percent
Number of Patients	XXX	XX.X%
Number of RHCs with comparative readings	XXX	XX.X%

Results will be presented using Bland-Altman comparing Sensor vs. Swan-Ganz.

Clinical Investigation Plan

[figure not shown]
Medication changes in response to PA pressure

Medication Changes in Response to PA Pressure	# Medications	
	N	Percent
ACE/ARB	XXX	XX.X%
Aldosterone Antagonist	XXX	XX.X%
Beta-blocker	XXX	XX.X%
Diuretic-Loop	XXX	XX.X%
Diuretic-Thiazide	XXX	XX.X%
Hydralazine	XXX	XX.X%
Nitrate	XXX	XX.X%
Other	XXX	XX.X%
Total	XXX	XX.X%

This confidential document is the property of Abbott and shall not be reproduced, distributed, disclosed or used without the express written consent of Abbott

Clinical Investigation Plan

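### Compliance is total readings over days at home, with no one-per-day or home-only limit, so it can exceed 100% and can misstate use in either direction.

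*Combined protocol and SAP*

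**What the plan says.** Section 12.7.2 gives the counting rule: "The total number of PA pressure readings taken will be reported as a percentage of patient days at home". The synopsis has the same ratio: "The total number of pulmonary artery (PA) pressure readings taken will be reported as a percentage of patient days at home". Section 10.2.3 names the topic without a formula: "Patient device usage over the course of the trial will be examined".

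The expected frequency is not fixed at once a day. According to the synopsis, "subjects will take PA pressure measurements on a daily basis, or as directed by the investigator".

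Readings away from home are foreseen in three places. Section 4.4 says "The data can be recorded from the home, hospital" and goes on to list the physician's office and the clinic. Section 8.5, on subjects who are hospitalized, in the ER or at a clinic visit, says "the CardioMEMS HF System may be used to obtain pulmonary artery pressure measurements at the investigators discretion". Section 8.3, on follow-up visits, says "PA pressure measurements may be obtained at the Investigator's discretion".

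Two places bear on how compliance is summarized. Section 12.7 sets a general rule for effectiveness analyses: mean, SD, median and range, as appropriate. Appendix L contains a table headed "Weekly Patient Pressure Reading Compliance", with rows for mean with SD and for median. Neither place gives a formula for compliance, and neither refers to the ratio in 12.7.2.

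**The concern.** A compliance percentage is normally read as the share of days on which the patient did what was asked. The ratio in 12.7.2 is not that. Two readings on one day count twice against a single home day. An inpatient reading, if counted, enters the numerator while its day is absent from the denominator, so a patient who is admitted more could appear more compliant. Everyone in this study had a heart failure hospitalization in the year before baseline, so inpatient days are to be expected. Patients told to read less than daily are pulled the other way: they can follow their instructions fully and still score well below 100%.

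The text does not say whether the ratio is one pooled figure or a value per patient. Two analysts could therefore report different compliance figures from the same data, each within the plan.

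Section 14 lists patient compliance among the items sent to FDA in the periodic updates and carried into the device labeling. Readings are also how the system exerts any effect, so a reader of this single-arm study will use the compliance figure to interpret the effectiveness result.

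**Working it through.** The documents give no compliance value, target, repeat-reading rate or non-user rate, so there is no figure of the plan's own to reproduce. Every input below is an assumption, chosen to show how the ratio behaves; none is an estimate.

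**1. Repeat readings.** Let a fraction f of patients never read and let the rest take m readings on every home day, with equal home days per patient.

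- Ratio in 12.7.2 = 100 × (1 − f) × m.
- Share of home days with at least one reading = 100 × (1 − f), for m of 1 or more.

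| f | m = 1.0 | m = 1.1 | m = 1.25 | m = 1.5 | Home days with a reading |
|---|---|---|---|---|---|
| 10% | 90% | 99% | 112.5% | 135% | 90% |
| 20% | 80% | 88% | 100% | 120% | 80% |
| 30% | 70% | 77% | 87.5% | 105% | 70% |

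For f = 20% and m = 1.25: 100 × 0.8 × 1.25 = 100%, while 80% of home days have a reading.

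**2. Inpatient readings, if counted.** Let c be the true share of home days with one reading, H the hospital days per year and r the readings per hospital day.

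- Ratio = 100 × [c × (365 − H) + H × r] / (365 − H).
- c = 80%, H = 5, r = 1: (288 + 5) / 360 = 81.4%.
- c = 80%, H = 20, r = 3: (276 + 60) / 345 = 97.4%.
- c = 100%, same two cases: 365 / 360 = 101.4% and 405 / 345 = 117.4%.

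**3. Less-than-daily direction.** A patient directed to read k times a week who does exactly that scores 100 × k / 7:

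- k = 3: 42.9%
- k = 2: 28.6%
- k = 1: 14.3%

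Here the ratio understates adherence to what was asked.

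**4. Pooled or per patient.** With f = 20% and m = 1.25, the pooled ratio is 100%. The same ratio calculated per patient has mean 100%, SD 50, median 125% and minimum 0%. A per-patient summary would therefore reveal the non-users, but its mean stays inflated unless each day is counted once.

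**The case against.** The strongest reply is that this is a small definitional gap that invites overstatement. Five parts of that reply deserve weight.

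- **Non-users.** A reader might infer that heavy users will hide non-users. That requires a single pooled figure as the only output. The reference to a total number suggests pooling but does not state it. Section 12.7 provides for mean, SD, median and range as appropriate, and Appendix L plans a mean, SD and median. Some spread may well be shown. This stands, and the masking is conditional on pooling.
- **Hospital readings.** A reader might infer that the numerator includes them. The 12.7.2 sentence concerns patient device usage and is scaled to days at home, so a home-only intention is plausible, and Sections 4.4 and 8.5 describe separate hospital electronics. The documents do not say either way. What remains is that the rule as worded does not exclude them.
- **Direction.** A reader might infer that compliance will be overstated. Because the frequency may be as directed, the net bias could go either way.
- **Appendix L.** A reader might infer that its table is a different quantity. It has no formula, so it may be the same ratio by patient-week. The supportable statement is that it is undefined and not linked. The regulatory and labeling updates run through this table, so the 12.7.2 sentence is not the only text that needs a definition.
- **Importance.** The measure is descriptive and supplemental, with no hypothesis, alpha or success criterion. This stands.

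None of this supplies the missing counting rule. A percentage that can exceed 100% when followed literally is not well defined, whichever of these readings was intended.

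**Conclusion.** The point holds in a limited form. As written, the ratio can overstate the share of home days with a reading and can exceed 100%. It can also understate adherence where a less-than-daily frequency was directed. If it is pooled, it does not show how many patients never read, and the Appendix L table is not defined well enough to fill that gap with certainty.

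The size of the bias is unknown. In the central illustration (20% non-users, the rest at 1.0 to 1.5 readings per day) the ratio is 80% to 120% against 80% of home days with a reading. Counted inpatient readings could lift a true 80% to between 81.4% and 97.4%, assuming 5 to 20 hospital days a year at 1 to 3 readings a day. These figures show what the formula permits and do not predict what the study will report. The documents do not support the statement that compliance will be overstated, only that it can be.

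This is a low-priority improvement. No primary hypothesis, sample size or error rate is affected.

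**What to change.** Replace the sentence in 12.7.2, and its counterpart in the synopsis, with a definition along these lines:

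- For each patient, compliance is the number of home days with at least one home reading divided by the number of days at home. Readings taken in hospital, ER or clinic are excluded. The result cannot exceed 100%, so no cap is needed.
- Report the mean, SD, median, minimum and maximum across patients, and the share of patients with no readings.
- Use the same definition for the Appendix L table, stating how it is applied by week.
- Note beside the result that, for patients directed to read less than daily, the figure measures daily use and not adherence to the directed schedule.

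In the illustrations of repeat and inpatient readings this definition returns the true share of home days with a reading. It does not remove the understatement for less-than-daily patients, which is why the note is needed.

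The cost is minor extra programming and a figure that may look less favourable. It assumes that the database holds reading dates and a label separating home from hospital or clinic readings; the documents say that measurements are transmitted automatically but do not confirm those fields. No new visits or assessments should be needed.
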